1.2 Secondary Objectives

- 1.2.1 To determine if pre-metastatic niche density in regional LNs is associated with PFS
- 1.2.2 To determine if therapy with axitinib prolongs time to biochemical recurrence
- 1.2.3 To determine if pSTAT3 in tumor tissue is associated with biochemical recurrence
- 1.2.4 To determine if myeloid derived suppressor cell (MDSC) recruitment in tumor tissue is associated with biochemical recurrence
- 1.2.5 To determine if lysyl oxidase (LOX) expression in tumor tissue is associated with biochemical recurrence
- 1.2.6 To evaluate time to metastatic recurrence
- 1.2.7 To determine the rate of erectile dysfunction and urinary incontinence (grade ≥ 3 for both) in the setting of preoperative axitinib therapy
- 1.2.8 To evaluate changes in blood-based biomarkers (pSTAT3 and selected angiogenic factors) from baseline to the time of prostatectomy

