9.0 Correlative/Special Studies

9.1 Laboratory Correlative Studies

Analysis of pre-metastatic niche density will take place through previously reported techniques. Briefly, a total of 12 4 μ m sections of benign lymph node tissue (derived from paraffin-embedded sections) will be stained with monoclonal antibodies directed at VEGFR1 (ImClone Systems). VEGFR1 clustering will be counted within 8 distinct 40x fields, and the cluster count will be averaged.

Analysis of pSTAT3 and related mediators will be conducted through previously reported techniques. Briefly, 4 mm sections of tumor tissue (derived from paraffin-embedded sections) will be stained with monoclonal antibodies directed at IL-6R (Calbiochem) and pSTAT3 (Santa Cruz Biotechnology). Using both IPLAB and Adobe Photoshop 7.0, random x100 objective fields will be analyzed by selected a standardized color range for immunohistochemical staining. After boundary delineation, the area under the pixilation histogram will be calculated, and the total staining area will be compared to the area of total tissue.

Of note, the laboratory investigator ([name], [name], or associates) will be blinded to the patient randomization. A total of 12 unstained slides derived from tumor and 12 unstained slides derived from normal lymph node tissue will be requested. These slides will be marked with a unique patient identifier number (UPIN) designated by the pathology core facility. Only the study PI and biostatistician will have access to the data to correlate UPIN with patient identification; this data will be housed in a password-protected electronic database.

Blood (a total of 20 mL) will be obtained at baseline, at the time of prostatectomy and at a follow-up visit 4 weeks following the procedure for correlative studies to examine levels of pSTAT3 in PMBCs and selected angiogenic markers. A total of 10 mL will be collected in a CPT tube (for PBMC isolation), and a separate aliquot of 10 mL will be collected in an EDTA tube (for assessment of angiogenic markers) at

the specified times of collection. Blood will be delivered to the lab of [name] (Beckman Research Institute, Room 3220) within four hours of collection.

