14.0 Statistical Considerations

14.1 Study Design

14.1.1 The study is an open label, randomized phase II assessment of axitinib as pre-surgical therapy in high risk prostate cancer. In particular, a permuted block randomization scheme will be carried out to achieve treatment/control balance. To avoid selection bias, the blocking scheme will be masked to the principal investigator. The number of blocks will be determined by stratifying high risk patients according to PSA levels (≥ 20 or not) and Gleason scores (≥ 8 or not). For each block, we will randomly choose one arrangement from all possible realizations.*Primary Endpoints*: The primary endpoint of this study is pre-metastatic niche density, as defined by the average number of VEGFR1 clusters in 8 distinct 40x microscopic fields. We will use a two sample student's T-test to compare the primary endpoint of pre-metastatic niche density in the regional lymph nodes of patients treated with axitinib, as compared to the pre-metastatic niche density in the lymph nodes of patients enrolled on the control arm. With a sample of 22 patients per group, we will have 80% power to determine significance across groups if the average niche density is 3.13 in patients in the control arm, and at most 2.19 in patients treated with axitinib, with a common standard deviation 1.43 using a one-sided t-test assuming a type I error = 10% (Calculated using nQuery Advisor 6.01) Taking this into consideration, 30 patients per group will be recruited according to an empirical replacement rate of 27%. The intention-to-treat analysis will be the primary analysis conducted to obtain unbiased comparisons between the treatment and control. In addition, some as-treated subgroup analysis would also be investigated if necessary.*Secondary Endpoints*: Toxicity, time to biochemical recurrence, time to metastatic recurrence. With respect to secondary endpoints, Cox regression will be used (with the log-rank test) to compare time to biochemical recurrence (PSA ≥ 0.2), TTP and OS in patients treated with axitinib to patients treated with surgery alone. The Chi-square test will be used to compare the pStat3, LOX expression and MDSC density in patients treated with axitinib to patients treated with surgery alone. Descriptive statistics will be used to compare serum levels of VEGF-A, sVEGFR2, PDGF-AB and pSTAT3 at various timepoints during therapy.

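### The between-arm chi-square test of tumour pSTAT3, LOX and MDSC density has no defined categories and does not fit pSTAT3 as measured; a rank-sum test would avoid an unspecified cut and the power it costs

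*Combined protocol and SAP*

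**What the plan says.** Under secondary endpoints, section 14.1.1 states: "The Chi-square test will be used to compare the pStat3, LOX expression and MDSC density in patients treated with axitinib", the comparator being surgery alone. It gives no categories, cut-points, significance level, sidedness, effect size or power for this comparison.

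Section 9.1 describes the tissue pSTAT3 assay as image analysis of stained sections, in which "the area under the pixilation histogram will be calculated, and the total staining area will be compared to the area of total tissue". It gives no tissue assay, unit or scoring scale for LOX or MDSC.

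The marker objectives in section 1.2 concern recurrence rather than arm differences, for example "To determine if pSTAT3 in tumor tissue is associated with biochemical recurrence" and "To determine if lysyl oxidase (LOX) expression in tumor tissue is associated with biochemical recurrence". The arm comparison therefore appears only in the statistical section.

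The same section analyses the primary endpoint, niche density, on its full scale with a two-sample t-test.

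**The concern.** The named test and the documented measurement do not match. An area fraction has no categories, so someone must create them before a chi-square test can be run, and the plan does not say how. Two things follow.

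- **Lost information.** Two men on the same side of the cut count as identical however far apart their values are. With 22 to 30 men per arm, that loss can matter.
- **Dependence on the cut.** With no cut fixed in advance, the result can change with the threshold chosen. Section 9.1 blinds the laboratory, but the principal investigator and the biostatistician hold the link between slide identifier and patient, and the trial is open-label. Laboratory blinding therefore does not settle how the cut is chosen.

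At stake is the reading of the mechanism. Sections 2.5 and 2.6 build the rationale on Stat3-driven MDSC recruitment, and this is the only formal between-arm test planned for those markers; the blood markers are summarised descriptively. A null result from a needlessly weak test could be read as evidence against the mechanism.

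**Working it through.** **1. Inputs.** All come from the primary endpoint in section 14.1.1, because the markers have none of their own.

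- Means: "if the average niche density is 3.13 in patients in the control arm, and at most 2.19 in patients treated with axitinib".
- Spread and level: "with a common standard deviation 1.43 using a one-sided t-test assuming a type I error = 10" per cent.
- Numbers: "With a sample of 22 patients per group, we will have 80% power to determine significance across groups"; then "30 patients per group will be recruited according to an empirical replacement rate of 27" per cent.

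Assumption: a marker shifts by the same standardised effect, with normal data. d = (3.13 − 2.19)/1.43 = 0.94/1.43 = 0.657.

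**2. Reproduce the plan's figure.** The noncentrality is d√(n/2) = 0.657 × √11 = 2.18 on 42 degrees of freedom. The noncentral t distribution gives 81.0% power at one-sided 10%, against the stated 80%. Also 22/(1 − 0.27) = 30.1, so 30 per arm reproduces. At 30 per arm the same t-test has 89.4%.

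**3. Chi-square after a pooled-median split** (uncorrected; simulated, 100,000 or more trials per setting).

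| Per arm | Level | t-test | Chi-square | Nominal loss |
|---|---|---|---|---|
| 22 | one-sided 10% | 81.0% | 59.2% | 21.8 |
| 22 | two-sided 5% | 56.8% | 34.6% | 22.2 |
| 30 | one-sided 10% | 89.4% | 77.2% | 12.2 |
| 30 | two-sided 5% | 70.7% | 58.5% | 12.2 |

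**4. Match for true size.** The split test is discrete. If k of the n control patients lie above the pooled median, z = [(2k − n)/n]/√(0.5/n), and under the null k is hypergeometric.

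- 22 per arm, one-sided 10%: k = 13 gives z = 1.21, below 1.28, so rejection needs k ≥ 14. True size 6.5%.
- 22 per arm, two-sided 5%: k = 14 gives 1.81, below 1.96, so rejection needs k ≥ 15 or the mirror image. True size 3.4%.
- 30 per arm, one-sided 10%: rejection needs k ≥ 18. True size 9.8%.
- 30 per arm, two-sided 5%: k = 19 gives 2.07, above 1.96. True size 7.0%.

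Running the t-test at those true sizes gives:

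- 22 per arm: 73.9 − 59.2 = 14.7 points (one-sided) and 49.9 − 34.6 = 15.3 (two-sided).
- 30 per arm: 89.2 − 77.2 = 12.0 points (one-sided) and 75.7 − 58.5 = 17.2 (two-sided).

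So about 7 of the 22 points at 22 per arm are conservatism of the split test. At 30 per arm, two-sided, the nominal 12 understates the loss.

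**5. Cross-check with a fixed cut.** A cut midway between the arm means gives proportions Φ(0.657/2) = 62.9% and 37.1%. The normal-approximation power of the two-proportion test at one-sided 10% is 67.1% (22 per arm) and 77.0% (30 per arm), a loss of 13.9 and 12.4 points. This agrees with step 4.

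**6. Sensitivity.**

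- Midpoint cut, effect 0.3 SD: 4 to 9 points lost.
- Midpoint cut, effect 1.2 SD: about 1 to 10 points lost.
- Cut near the upper quartile (31.9% v 13.0%), effect 0.657, one-sided 10%: 21.9 points (22 per arm) and 20.6 (30 per arm).
- Extreme cut (17.1% v 5.4%), effect 0.657, 30 per arm, one-sided 10%: about 33 points.

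**7. The alternative.** Simulated Wilcoxon rank-sum power against the t-test, effect 0.657:

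- Normal data, one-sided 10%: 79.4% v 80.6% (22 per arm); 88.2% v 89.2% (30 per arm).
- Normal data, two-sided 5%: 54.4% v 56.6%; 68.4% v 70.6%.
- Lognormal data, one-sided 10%: 79.4% v 70.9%; 88.2% v 79.7%.

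**The case against.** Four points can fairly be made for the plan.

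- **The comparison is minor.** It is not a listed objective: 1.2.3 to 1.2.5 concern recurrence. The markers are not among the listed secondary endpoints, and no power is claimed for them. Blood pSTAT3 is also measured at three time points, so the tissue test is not the only evidence on mechanism. This stands and limits the weight of the point. It does not make the stated test workable.
- **The markers may not all be continuous.** A reader might infer that the plan forces three continuous measures into categories. The documents support this for pSTAT3 only. It is implied by the word *density* for MDSC, and LOX expression could be a categorical score. This stands.
- **The power loss is not the plan's.** A reader might take 12 to 22 points as a property of this design, all of it lost information. The documents give no effect, level or cut for these markers, so the figure is borrowed, and part of it is discreteness (step 4). This stands.
- **A t-test is not automatically the remedy.** A reader might infer that either a t-test or a rank test would keep the power. With lognormal data the t-test falls to 70.9% at 22 per arm. A rule to switch to a rank test if the data look skewed would again leave the choice until after the data are seen.

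Nor do the documents show that a cut would be picked to favour a result. They only leave it open.

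**Conclusion.** The point holds in a limited form. For tissue pSTAT3 the stated chi-square test cannot be run as the measure is described without an unspecified cut, and a better test is available at almost no cost. For MDSC the same is likely. For LOX the plan does not give enough to tell.

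The size is conditional. It assumes the primary endpoint's 0.657 SD, normal data and a pooled-median split, at one-sided 10% or two-sided 5%. The nominal loss is then about 12 points at 30 per arm and 22 at 22 per arm, or about 12 to 17 when matched for true size. Across other effects and cuts it runs from about 1 to over 30 points.

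The primary niche-density analysis does not use this test, so its conclusion is unaffected. This is a worthwhile correction to a secondary analysis, not a threat to the trial.

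**What to change.** In section 14.1.1, replace the chi-square sentence with:

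*pSTAT3 (stained area / tissue area), MDSC density and LOX expression will be compared between randomised arms on their measured or ordered scale with the Wilcoxon rank-sum test, reporting the shift estimate with its confidence interval; any high/low table is descriptive only.*

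Keep chi-square only for a marker recorded solely as binary or unordered categories. To make this usable, state the scale of LOX and MDSC in section 9.1, and give the significance level and sidedness of the comparison.

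The cost is a few sentences, with no new patients. If the data are exactly normal, the rank test gives up about 1 to 2 power points against the t-test in the runs above; allowing up to 4 would be cautious. A shift estimate is also less familiar to readers than a percentage, which can still be tabulated.

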6.1.1 Schedule

In patients on the experimental arm, axitinib should be taken at a dose of 5 mg oral bid, with 28 days of therapy constituting 1 cycle.

The date of initiation of axitinib therapy will be contingent upon the date selected for prostatectomy and pelvic lymph node dissection, with 28 days of planned therapy to conclude 48 hours prior to surgical intervention.

In patients on the control arm, no systemic therapy will be instituted. Rather, prostatectomy and pelvic lymph node dissection will be carried out within 5-6 weeks after biopsy confirmation of prostate cancer.

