7.1 Axitinib Dose Reduction for Hypertension

In sponsored studies, patients treated with axitinib were issued blood pressure cuffs for home monitoring and instructed to measure their blood pressure (BP) twice daily, prior to taking each dose. All blood pressure measurements were recorded in a diary and brought to the nurse or study coordinator at each clinic visit. Patients were instructed by the study staff to contact their physician immediately for guidance if their systolic blood pressure rises above 150 mm Hg, diastolic blood pressure rises above 100 mm Hg, or if they develop symptoms perceived to be related to elevated BP (eg, headache, visual disturbance). See below for dose modifications for hypertension.

New or additional antihypertensive therapy (See Section 6.6.3, Concomitant Medication(s) for guidance) should be started if 2 BP readings, preferably taken in the clinic and separated by at least 1 hour, show the following: 2 systolic BP readings greater than 150 or 2 dBP readings greater than 100 mm Hg. Alternately, the dose of existing antihypertensive medication(s) may be increased. If the patient is already on maximal antihypertensive treatment, the axitinib dose should be reduced by 1 dose level.

Patients who have 2 systolic BP readings, separated by at least 1 hour, greater than 160 mm Hg, or 2 dBP readings, separated by at least 1 hour, greater than 105 mm Hg, should have treatment with axitinib held. (Note: if axitinib is held, patients receiving antihypertensive medications should monitor closely for hypotension and restart axitinib at one lower dose level as soon as BP is $<150/100$ mm Hg. Plasma half-life of axitinib is 2 – 4 hours and BP usually decreases within 1-2 days following dose interruption.) Treatment with axitinib should be restarted at 1 lower dose level as soon as the systolic blood pressure reduces to less than 150 mm Hg and the dBP reduces to less than 100 mm Hg.

Patients who develop recurrent systolic hypertension (2 BP readings separated by at least 1 hour show systolic pressure >150 mm Hg) or recurrent diastolic BP >100 mm Hg following previous axitinib dose reduction should undergo another dose reduction by one dose level.

Patients removed from treatment for intolerable toxicity should still be followed with regular tumor assessments until disease progression or start of new treatment, and for survival thereafter. Guidance on dose interruption and reduction for hypertension is summarized in the table below.

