10.2 Study calendar for patients randomized to observation

	Pre-Study	Wk 1	Wk 5	Wk 9	Wk 21	Wk 33	Wk 45	Wk 57	Wk 69	Off Study
Axitinib 5 mg oral bid ^a										
Prostatectomy/PLND				X						
Informed Consent		X								
Demographics		X								
Medical history		X								
Concurrent meds		X								
Physical exam ^e	X		X	X	X	X	X	X	X	X
Vital signs	X		X	X	X	X	X	X	X	X
Height	X									
Weight	X		X	X	X	X	X	X	X	X
Performance Status	X		X	X	X	X	X	X	X	X
CBC w/diff, plts*	X		X	X	X	X	X	X	X	X
Serum chemistry ^{b*}	X		X	X	X	X	X	X	X	X
Lipid panel (with LDL)*	X									
Thyroid function tests (TSH, fT4)*	X									
PT, PTT, INR*	X									
PSA*	X		X	X	X	X	X	X	X	X
Correlative blood (Section 9.1)	X		X	X						
Adverse event evaluation									X	
Bone scan (section 4.1.1)	X									
CT/MRI(section 4.1.1)	X									
UA ^{f*}	X									X
Collection of tumor specimens (Section 9.1)				X						

a: Excepting adjustments for toxicity. b: Albumin, alkaline phosphatase, total bilirubin (direct bilirubin should be obtained level is $>1.5 \times$ ULN), bicarbonate, BUN, calcium, chloride, creatinine, glucose, LDH, phosphorus, potassium, total protein, SGPT[ALT], GGT, sodium. c: After week 81, on study, continue assessments noted at weeks 9, 21, and 33 every 12 weeks biochemical recurrence. d: Off-study evaluation. e: Patients will be supplied with a blood pressure cuff. At the specified in 2 and week 4 of axitinib therapy), the study nurse will call the patients to obtain blood pressure data and report any abnormal to the treating clinician. The treating clinician will dictate a progress note incorporating these data using the template in Appendix 2. If proteinuria is $\geq 2+$ for protein then a 24-hour urine collection can be done and the patient may enter only if urinary protein is <2 g per 24 hours. f: Clinic visits and laboratories prior to week 9 may be performed/collected within ± 3 days of the dates specified in the study calendar. From week 9 onwards, all clinic visits and laboratories may be performed/collected within ± 7 days of the dates specified in the study calendar. Pre-study labs may coincide with day 1 labs if performed within ± 3 days.

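### The blood-marker analysis describes serum levels during therapy, but no draw falls during dosing and the samples are plasma and PBMCs; a baseline-adjusted between-arm estimate would be a free improvement

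*Combined protocol and SAP*

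**What the plan says.** The objective, 1.2.8, is "To evaluate changes in blood-based biomarkers (pSTAT3 and selected angiogenic factors) from baseline to the time of prostatectomy". The synopsis repeats it.

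The only analysis statement is the last sentence of Section 14.1.1: "Descriptive statistics will be used to compare serum levels of VEGF-A, sVEGFR2, PDGF-AB and pSTAT3 at various timepoints during therapy". It names no arms, contrast, model or baseline adjustment. Just before it, the time-to-event endpoints are compared by arm with Cox regression and the log-rank test, and the tissue markers also get a named test and named arms: "The Chi-square test will be used to compare the pStat3, LOX expression and MDSC density in patients treated with axitinib", set against surgery alone.

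On sampling, Section 9.1 says that blood "will be obtained at baseline, at the time of prostatectomy and at a follow-up visit 4 weeks following the procedure", and Section 6.3 gives the same three draws. Section 9.1 assigns VEGF-A, PDGF-AB and soluble VEGFR-2 to plasma by ELISA, and pSTAT3 to PBMCs isolated from a CPT tube.

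On treatment, Section 6.1.1 schedules axitinib "with 28 days of planned therapy to conclude 48 hours prior to surgical intervention", and Section 6.1.2 allows a single cycle. For controls, Section 6.1.1 says "In patients on the control arm, no systemic therapy will be instituted". The observation-arm calendar (Section 10.2) nevertheless carries a row for "Correlative blood (Section 9.1"), as does the axitinib calendar (Section 10.1).

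**The concern.** The analysis sentence does not describe the data that the trial will hold. Its timepoints do not exist in the schedule, its sample type is not the one assayed, and its reference to therapy has no meaning in the control arm.

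It also leaves the comparison open. The interval between baseline and prostatectomy includes waiting time and preparation for surgery as well as 28 days of axitinib. A shift in a marker within the axitinib arm could come from any of these. The randomised control arm is what allows the drug's contribution to be estimated, and its blood is already scheduled. If no contrast is fixed in advance, the choice of comparison is left until the data are in. An obvious ad hoc choice, the raw change score, can be less precise than ignoring baseline altogether.

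**Working it through.** **1. Timing of the draws.** The last planned dose is 48 hours before surgery (Section 6.1.1). On half-life, Section 7.1 says "Plasma half-life of axitinib is 2 – 4 hours and BP usually decreases within 1-2 days following dose interruption".

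- 48 h / 4 h = 12 half-lives; 48 h / 2 h = 24 half-lives.
- With the shorter minimum interruption of 24 hours that Section 7.2 gives for surgery, 24 / 4 = 6 to 24 / 2 = 12 half-lives.

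Either way the prostatectomy draw follows the last dose. Baseline precedes the first dose, and the third draw is 4 weeks after surgery. Scheduled draws during dosing: none of three.

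**2. Sample type.** Section 14.1.1 says serum for all four markers. Section 9.1 says plasma for three and PBMCs for pSTAT3. None of the four matches.

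**3. Both arms sampled.** I rely on the correlative-blood row being present in both calendars, not on the week columns, whose alignment is unreliable in the available text. Sections 6.3 and 9.1 do not restrict blood collection to one arm.

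**4. The plan's own figure.** There is none for the blood markers. The 22 per arm comes from the primary endpoint: means 3.13 and 2.19 (difference 0.94), SD 1.43, one-sided 10%. The noncentral t gives 81.0% power at 22 per arm against the stated 80%, so that figure reproduces. I use 22 only as a plausible number of complete pairs. Section 14.1.1 plans to recruit 30 per arm.

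**5. Precision of a between-arm estimate, in SD units of the marker.** Let ρ be the correlation between the baseline and prostatectomy values. The documents do not give ρ, so the values below are assumptions.

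- Prostatectomy value alone: half-width = t(0.975, 2n−2) × √(2/n). For n = 22: 2.018 × √(2/22) = 2.018 × 0.3015 = 0.61.
- ANCOVA: multiply the variance by (1 − ρ²), with one fewer degree of freedom.
- Raw change score: multiply the variance by 2(1 − ρ). This exceeds 1 when ρ is below 0.5.

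| ρ (assumed) | ANCOVA variance factor | Reduction | Half-width, n = 22 | Half-width, n = 30 |
|---|---|---|---|---|
| no adjustment | 1.00 | none | 0.61 | 0.52 |
| 0.3 | 0.91 | 9% | 0.58 | 0.49 |
| 0.5 | 0.75 | 25% | 0.53 | 0.45 |
| 0.7 | 0.51 | 49% | 0.43 | 0.37 |

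At ρ = 0.3 the change-score factor is 2 × 0.7 = 1.4, which is worse than using no baseline. The two stratification factors would cost a further two degrees of freedom, a small effect.

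**The case against.** The best defence is that description is a legitimate choice here. The blood markers are correlative studies in a small phase II trial, nothing is powered on them, and neither the synopsis nor Section 14.1.1 lists them among the secondary endpoints. Objective 1.2.8 asks for change from baseline to prostatectomy and mentions no arms, so a summary of change satisfies it as worded. That stands. It is why the ANCOVA is offered as an improvement.

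Several stronger readings are tempting and are not supported:

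- *The baseline and control samples go unused.* This would be inferred from silence. The sentence excludes neither, change from baseline necessarily uses baseline, and control values could be tabulated by arm. What is missing is a stated contrast and adjustment.
- *The surgery sample is uninformative because the drug has cleared.* The half-life concerns axitinib in plasma. The documents give no kinetics for any of the four markers, and an effect of 28 days' treatment may persist.
- *An off-drug value will be reported as on-drug.* The draw times and the washout are set out plainly elsewhere, so the documents do not show this.

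The precision figures also have limits. They compare two analyses, neither of which is in the plan, and they assume complete pairs, while Section 9.1 discards CPT samples that arrive after 4 hours. Multiplicity counts too: four independent tests at 5% would give 1 − 0.95⁴ = 18.5% familywise error. These points shape the fix. They do not rescue the timepoint and sample-type wording.

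**Conclusion.** The concern holds in two parts of different weight.

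- **Definite:** the timepoints and the sample type in the blood-marker sentence contradict Sections 6.1.1, 6.3 and 9.1 and need correcting. This part rests on no assumption beyond the planned schedule.
- **Improvement:** a baseline-adjusted comparison of the randomised arms would separate an axitinib effect from the passage of time, using samples already scheduled. The gain in precision depends on the undocumented correlation: with 22 complete pairs per arm, the half-width falls from 0.61 SD to 0.53 SD at 0.5 or 0.43 SD at 0.7, and the variance falls by only 9% at 0.3. Even with little gain in precision, the controlled contrast is worth having.

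The quantity estimated would be a post-washout effect and should be described as such.

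**What to change.** 1. Replace the sample and timepoint wording in Section 14.1.1 with: *plasma VEGF-A, PDGF-AB and sVEGFR-2 and PBMC pSTAT3 at baseline, at prostatectomy (after the planned 48-hour washout) and 4 weeks after surgery.*

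2. Add: *For each marker, the prostatectomy value (log scale if skewed) will be compared between randomised arms by ANCOVA adjusting for baseline and the PSA and Gleason stratification factors, in all randomised patients with both samples. The adjusted difference or ratio will be reported with a 95% CI, labelled exploratory, without multiplicity adjustment. The 4-week post-operative value will be summarised in the same way.*

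3. Report the number of missing and discarded samples by arm. If logs are used, say how values below the assay's detection limit are handled.

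The cost is a few sentences and four simple models at each of two timepoints (eight in all). No patients, visits or blood draws are added. The downside is a handful of extra exploratory estimates, which the label and intervals should keep in proportion.

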13.0 Data and Safety Monitoring Plan

DATA AND SAFETY MONITORING

13.1 *Definition of Risk Level*

This is a Risk Level 4 study, as defined in the “City of Hope Data and Safety Monitoring Plan”, <http://www.coh.org/dsmc/Pages/forms-and-procedures.aspx> involving a COH-held IND.

13.2 *Monitoring and Personnel Responsible for Monitoring*

The Protocol Management Team (PMT) consisting of the PI, Collaborating Investigator, CRA/protocol nurse, and statistician is responsible for monitoring the data and safety of this study, including implementation of the stopping rules for safety and efficacy.

Data and safety will be reported to the COH DSMC. Protocol specific data collection will include the following items: Adverse event reporting and quarterly safety assessment of axitinib. Reporting of data and safety to the DSMC will occur at least quarterly using the PMT report.

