14.1.2 *Stopping Rules.* Toxicity will be monitored on an ongoing basis. If the number of unacceptable toxicities exceeds 1 in the first 3 patients, or exceeds 2 in the first 6 patients or more than 25% thereafter, the study will hold accrual for an amendment regarding treatment modifications or study termination. Toxicity will be graded and recorded for each patient in this population according to CTCAE 4.0. Also, a delay in surgery exceeding 7 days as a consequence of axitinib-related toxicity will be considered an unacceptable toxicity.

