14.2 Sample Size Accrual Rate

The previously noted sample size of 60 patients is anticipated to accrue over the course of 60 months.

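### Read as a running count, the toxicity rule accepts 2 events in 6 patients (33.3%) but requires an accrual hold at patient 7 even when that patient has no toxicity (2/7 = 28.6%)

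*Combined protocol and SAP*

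**What the plan says.** Section 14.1.2 (Stopping Rules) states: "Toxicity will be monitored on an ongoing basis". Its limits on unacceptable toxicities are worded this way: "exceeds 1 in the first 3 patients, or exceeds 2 in the first 6 patients or more than 25% thereafter". When a limit is crossed, "the study will hold accrual for an amendment regarding treatment modifications or study termination". The one event it names explicitly is surgical: "a delay in surgery exceeding 7 days as a consequence of axitinib-related toxicity will be considered an unacceptable toxicity".

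The section does not say whether the 25% is taken over all patients or only over those after the sixth, which patients are counted, or at what points the limit is checked. It gives no expected toxicity rate and no operating characteristics.

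Section 13.2 makes the Protocol Management Team, which includes a statistician, responsible for applying the stopping rules. It lists "Adverse event reporting and quarterly safety assessment of axitinib" and requires reporting to the monitoring committee at least quarterly.

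The patients counted are presumably those given axitinib, since section 6.1.1 says: "In patients on the control arm, no systemic therapy will be instituted". The size of that arm depends on the section. Section 14.1.1 recruits 30 per group, and section 14.2 says: "The previously noted sample size of 60 patients is anticipated to accrue over the course of 60 months". The synopsis and section 3.3 give 44 in total, or 22 per group.

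**The concern.** The first two limits are nested counts from the first patient onward: the first 6 include the first 3. The natural reading is that the third limit continues the same running count. On that reading the limit for six patients tolerates an observed rate of one third, and the limit that takes over at the seventh tolerates only a quarter. Two events that were acceptable at patient 6 therefore become a reason to stop at patient 7, although the only new information is a patient without toxicity.

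At stake is an accrual hold, with an amendment or a termination decision to follow, that no new safety signal has prompted. The trial runs at one site and plans 60 patients over 60 months, so such a hold has a cost.

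**Working it through.** The plan states no figure for how this rule performs, so there is none to reproduce. The check starts from the wording of the rule.

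**Step 1. The limit at each patient number.** Let x be the running number of events among the first n patients. Hold if x > 1 for n = 1 to 3, if x > 2 for n = 4 to 6, and if x/n > 0.25 (that is, 4x > n) for n ≥ 7.

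| n | Smallest count that holds |
|---|---|
| 1–3 | 2 |
| 4–6 | 3 |
| 7 | 2 |
| 8–11 | 3 |
| 12–15 | 4 |
| 16–19 | 5 |
| 20–23 | 6 |
| 24–27 | 7 |
| 28–30 | 8 |

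The holding count falls only once, at n = 7.

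**Step 2. The step itself.**
- n = 6, x = 2: 2/6 = 33.3%. The count does not exceed 2, so accrual continues.
- n = 7, x still 2: 2/7 = 28.6%, more than 25%, so accrual is held.
- n = 8, x = 2: 2/8 = 25.0%, not more than 25%, so within the limit. This compares boundaries only (see the objection).

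**Step 3. The other reading.** If the 25% counts only patients after the sixth, the step does not arise. With a check after each patient, however, one event among patients 7 to 9 forces a hold (1/1 = 100%, 1/2 = 50%, 1/3 = 33.3%).

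**Step 4. Chance of a hold at patient 7 with no new event.** The assumptions are: axitinib patients only, at most one event per patient, independent events with rate p, and a check after every patient. The rates are assumed because the plan gives none. Two events can fall among six patients in 15 ways. In 3 of these both fall in the first three patients, which would already have triggered a hold, leaving 12. Hence P = 12 p²(1 − p)⁵:
- p = 0.05: 12 × 0.0025 × 0.7738 = 2.3%
- p = 0.10: 12 × 0.01 × 0.5905 = 7.1%
- p = 0.15: 12 × 0.0225 × 0.4437 = 12.0%
- p = 0.20: 12 × 0.04 × 0.3277 = 15.7%

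**Step 5. Effect on the chance of any hold.** Let f(n, x) be the probability of x events at n with no hold so far. Then f(n, x) = (1 − p) f(n−1, x) + p f(n−1, x−1), set to zero wherever the rule holds. The chance of any hold by N is 1 − Σ f(N, x). The comparator leaves the holding count at 3 for n = 7. It serves only to measure the step and is not a proposal. It removes both routes to 2/7: an unchanged 2, and 1 of 6 followed by an event in patient 7.

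| Assumed rate | By 22: as written | By 22: without step | Difference (points) | By 30: as written | By 30: without step | Difference (points) |
|---|---|---|---|---|---|---|
| 5% | 5.0% | 2.2% | 2.8 | 5.0% | 2.2% | 2.8 |
| 10% | 18.4% | 11.9% | 6.5 | 18.6% | 12.2% | 6.4 |
| 15% | 37.2% | 29.4% | 7.8 | 38.4% | 30.9% | 7.5 |
| 20% | 57.0% | 50.2% | 6.8 | 59.8% | 53.6% | 6.1 |
| 30% | 86.1% | 83.2% | 2.8 | 89.7% | 87.7% | 1.9 |
| 40% | 97.4% | 96.8% | 0.6 | 98.7% | 98.5% | 0.3 |

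Differences are taken before rounding.

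**The case against.** The strongest defence is that nothing stated in section 14.1.2 is miscalculated. The two limits govern different patient numbers and never apply together. Tolerating more early and less later can be a deliberate tightening, and a dip at one patient number is a by-product of joining whole-number limits to a percentage. It is true that the limits never collide at the same n. But a deliberate tightening does not explain a holding count that goes from 3 to 2 and back to 3, and the section does not say that the dip is intended.

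The second objection concerns timing. Ongoing monitoring need not mean that the 25% limit is tested after every patient, and section 13.2 speaks of quarterly assessment. At 60 patients in 60 months, about 3 enter per quarter, or about 1.5 on axitinib, so a quarterly look could pass over n = 7. This stands as a limit on the probabilities, which are those of continuous checking. It does not remove the dip from the rule. It also tempers Step 3, which assumes checks after each patient.

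Third, section 14.1.2 counts toxicities rather than patients, and neither the event rate nor the counted population is given. The magnitudes therefore rest on assumptions.

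A reader might also infer that the trial would be held at patient 7 and then cleared at patient 8 on the same two events. The documents do not support that as the usual course: the hold stops accrual, so patient 8 is seen only if already enrolled or after accrual resumes.

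**Conclusion.** The rule is wrong as written, with low severity. On a running count checked as each patient is assessed, an unchanged 2 events goes from accepted at patient 6 to a required hold at patient 7, although the observed rate has dropped from 33.3% to 28.6%. It is the only such step from patient 1 to 30. Counting only patients after the sixth avoids the step but leaves a limit that one event can cross at patients 7 to 9 under the same checking.

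The size depends on assumed rates, a check after every axitinib patient and at most one event each. For rates of 5% to 20% the step adds 2.8 to 7.8 percentage points to the chance of any hold. That range must not be carried to higher rates: the addition is about 1.9 to 2.8 points at 30% and 0.3 to 0.6 at 40%.

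Two stronger conclusions are not supported. The step does not expose patients to extra risk, because it errs toward caution. Nor does it end the trial automatically, because the stated consequence is a hold pending an amendment or a termination decision.

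**What to change.** The sponsor should reconcile the six-patient and 25% limbs of section 14.1.2 so that a count accepted at patient 6 does not trigger a hold at patient 7 solely because a patient without toxicity was added. The same edit should state whether the 25% is cumulative from the first patient, which patients are counted, and when the limit is checked, in agreement with section 13.2. No threshold or clinical rule is proposed here; those are for the sponsor to set. The cost is protocol wording only, with no added patients or procedures.
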